1 PROTOCOL SUMMARY

Response to Influenza Vaccine During Pregnancy

Phase: IV

Population: Up to 50 healthy pregnant women ages 18-49 years

Intervention: Women will be vaccinated with the Quadrivalent, Inactivated Influenza Vaccine (IIV4) in Year 1 at Screening/Entry with subsequent visits at Day 7 and Day 28. No more than 60 mLs of blood will be collected from volunteers at each visit. In Year 2, participants will be vaccinated with IIV4 at Day 0. 60 mLs of blood will be collected at Day 0, Day 7, and Day 28 to compare immune response to influenza vaccination between the pregnant and non-pregnant states.

Number of Sites: 1

Study Duration: 60 months for enrollment, study completion, analysis

Subject Participation Duration: Approximately 56 weeks

Description of Agent or Intervention:

Quadrivalent, Inactivated Influenza Vaccine (IIV4)

Endpoint | **Primary**: HAI titers

Description of Study Design: This is a Phase IV study of healthy pregnant women who will receive the current seasonal IIV4 during two consecutive influenza seasons (second year while non-pregnant). Immunization will be at Screening/Entry in Year 1 and Day 0 in Year 2. Blood samples for immunogenicity assays will be collected at the time of immunization and at Days 7 (6-8) and 28 (21-35) in both Year 1 and Year 2.

Study Participants: Up to 50 pregnant women will be given seasonal IIV4 in two consecutive influenza seasons. Each volunteer will complete a total of 6 visits: Day 0, Day 7 and Day 28 in both Year 1 and Year 2.

Estimated Time to Complete Enrollment: Participants will be enrolled Aug-Jan until enrollment is complete; anticipated time = 2 years

2 ENDPOINTS

Primary: HAI Titers at Week 4 after vaccination

Secondary: Grade 2 or Higher Adverse Effects

3 BACKGROUND

Influenza virus infection represents a major cause of morbidity and mortality in the United States, resulting in 9.2-35.6 million illnesses, 140,000-710,000 hospitalizations, and 12,000-56,000 deaths annually since 2010 (1). This results in life-years lost, quality of life reduced. and an economic and medical cost of between \$71 billion and \$167 billion per year. Along with the fact that influenza can trigger deadly pandemics such as the 1918 pandemic that resulted in the deaths of 50 million to 100 million people (3-5% of the global population), these data illustrate the high level of priority needed to curb the public health threat of influenza. Influenza continues to be a problem due to the problems with the current vaccine strategy. Now our vaccines incorporate only three or four of the large number of circulating strains, with no adjuvant except for the elderly, and provide only 10-60% protection from influenza infection (2). Annual modifications of the vaccine are required each year, based on predictions of the next season's circulating strains. This strategy is often thwarted by the annual antigenic changes that occur in influenza virus composition. In addition to the issues with seasonal influenza, pandemic influenza typically starts with unpredicted strains, for which entirely new vaccines are required, significantly hindering our preparedness. These reasons and more highlight the necessity for a better understanding of the key components of an effective immune response and how this could lead to a universal vaccine. Pregnant women are known to have more severe influenza. In this study, we will investigate immunologic reasons to explain the increased morbidity/mortality associated with influenza in pregnant women

3.1 Potential Risks and Benefits

3.1.1 Potential Risks

This protocol will immunize adult participants with IIV4 (IM), which is recommended for use in the age groups and population studied. The discomforts of this study are those of receiving IM injection and blood drawn from an arm vein, and possible reactions to the vaccine. Drawing blood causes transient discomfort and may cause fainting. Infection at the site where blood will be drawn or where the vaccination is given is extremely unlikely but is a potential risk. Bruising at the site of blood drawing may occur, but can be prevented or lessened by applying pressure for several minutes immediately after the blood draw. Immediate allergic reactions to vaccine, including anaphylaxis, are extremely rare (approximately 1 person in 4,000,000), and might occur as a skin rash such as hives, difficulty breathing, fainting, drop in the blood pressure and death. Such reactions can usually be stopped by emergency medications administered by study personnel. Vaccine recipients may develop systemic reactions such as fever, headaches, body aches, and fatigue. These reactions are usually greatest within the first 24 to 72 hours after vaccination and last 1 to 2 days. Analgesics (e.g., aspirin or Tylenol®) and rest will generally relieve or moderate these symptoms. Other hypersensitivity reactions, including Arthus reactions resulting in large local swelling reactions, are also possible. Although Guillain-Barré syndrome may have been associated with the 1976-77 inactivated swine influenza vaccine and TIV vaccines used in early 1990's, subsequent inactivated vaccines have not been associated with an increased risk of this condition.

Participation in this study may involve risks to the participant which are currently unforeseeable.

3.1.1 Potential Benefits

Participants given the seasonal influenza vaccine are likely to experience decreased frequency and severity of subsequent influenza infection. The beneficial role of influenza vaccination has been recognized increasingly over the past several years as more information has become available about the high rate of morbidity and mortality from this respiratory pathogen.

4 STUDY DESIGN

This is a phase IV study of 50 healthy 18-49 year old pregnant women who will be given licensed seasonal IIV4. There are no exclusions for ethnicity or race. Following confirmation of written informed consent, baseline blood samples will be drawn from all study participants prior to immunization.

Intervention Group: Up to 50 healthy pregnant volunteers, 18-49 year old, will be given seasonal quadrivalent inactivated influenza vaccine (IIV4). Each volunteer will complete a total of 3 visits in Year 1: Day 0 (Screening/Entry/Immunization visit), and Day 7 +/- 1 and Day 28+/- 7 and a total of 3 visits in Year 2 (when not pregnant): Day 0 (Immunization visit), and Day 7 +/- 1 and Day 28 +/- 7 (post-immunization). All visits will consist of drawing blood for study assays and monitoring for serious adverse events (SAEs) and adverse events (AEs). In Year 2, if participant is pregnant, they will not be entered into Year 2 of the protocol.

5 STUDY ENROLLMENT AND WITHDRAWAL

5.1 Subject Inclusion Criteria

- 1. 18-49 year old pregnant woman
- 2. Willing and able to complete the informed consent process
- 3. Availability for follow-up for the planned duration of the study with the expected delivery date more than 8 weeks after vaccination (i.e., before 32 weeks gestational age of pregnancy)
- 4. Acceptable medical history by review of inclusion/exclusion criteria

5.2 Subject Exclusion Criteria

- 1. Prior off-study vaccination with seasonal influenza vaccine within three months of study entry.
- 2. Life-threatening reactions to previous influenza vaccinations.
- 3. Allergy to egg or egg products or to vaccine components including gentamicin, gelatin, or arginine.
- 4. Active systemic or serious concurrent illness, including febrile illness on the day of vaccination.
- 5. Hemoglobin <9 g/dL within the past 8 weeks (those without a value within that timeframe will have a Hdb drawn at entry).
- 6. History of immunodeficiency (including HIV infection).
- 7. Known or suspected impairment of immunologic function; may include significant liver disease, diabetes mellitus treated with insulin or moderate to severe renal disease
- 8. Chronic Hepatitis B or C.
- 9. Recent or current use of immunosuppressive medication, including systemic glucocorticoids (corticosteroid nasal sprays, inhaled corticosteroids, and topical corticosteroids are permissible). Use of oral steroids (≤10mg prednisone-equivalent/day) may be acceptable after review by the Protocol Director.
- 10. Malignancy (other than squamous cell or basal cell skin cancer) within the past 5 years.
- 11. Autoimmune disease (such as Rheumatoid arthritis, lupus, etc.) treated with immunosuppressive medication such as Plaquenil, methotrexate, prednisone, Enbrel.
- 12. Receipt of blood or blood products within the past 6 months or planned used during the study.
- 13. Receipt of an inactivated vaccine 14 days prior to study enrollment, or planned vaccinations prior to completion of last annual study visit.
- 14. Receipt of a live, attenuated vaccine within 28 days prior to enrollment or planned vaccination during post-vaccination follow-up.
- 15. Need for allergy immunization (that cannot be postponed) until after the last study visit.
- 16. History of Guillain-Barré syndrome.
- 17. Use of investigational agents within 30 days prior to enrollment or planned use during the study.
- 18. Donation of the equivalent of a unit of blood within 4 weeks prior to enrollment or donation of platelets within 2 weeks of enrollment or planned donation prior to completion of the last visit.
- 19. Any condition which, in the opinion of the investigator, might interfere with volunteer safety, study objectives or the ability of the participant to understand or comply with the study protocol.

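### The three-month look-back in exclusion 1 is shorter than the August to January enrolment season, so a woman already given that season's vaccine can enter with a raised Day 0 titre

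*Protocol*

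**What the plan says.** Item 1 of section 5.2 excludes "Prior off-study vaccination with seasonal influenza vaccine within three months of study entry". The Protocol Summary (section 1) gives the enrolment calendar: "Participants will be enrolled Aug-Jan until enrollment is complete". Section 4 makes the Day 0 sample the baseline: "baseline blood samples will be drawn from all study participants prior to immunization".

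Three other exclusions in section 5.2 could bear on an earlier dose:

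- Item 13 begins "Receipt of an inactivated vaccine 14 days prior to study enrollment". Its second limb concerns vaccinations still planned.
- Item 14 begins "Receipt of a live, attenuated vaccine within 28 days prior to enrollment". Its second limb also looks forward.
- Item 19 covers "Any condition which, in the opinion of the investigator, might interfere with volunteer safety, study objectives", among other grounds. It does not mention earlier vaccination.

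Section 7.6.3 records five years of influenza vaccination history but attaches no eligibility rule to it. Section 7.6.4 re-applies the exclusions at Day 0 of Year 2.

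The primary endpoint in section 2 is "HAI Titers at Week 4 after vaccination". Section 10.3 reports the percentage of women with a four-fold rise at Week 4 in each of the two years. Section 1 states the purpose of the two-year design as "to compare immune response to influenza vaccination between the pregnant and non-pregnant states".

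**The concern.** A four-fold rise is measured against Day 0. It describes the response to the study dose only if the Day 0 titre has not already been raised by the same season's vaccine. Item 1 appears meant to protect that baseline, but its window is about half as long as the enrolment season. A woman vaccinated in September who enters in January meets every written criterion.

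Such a woman starts from a raised titre and is less likely to rise four-fold, so she pulls that year's percentage down. If more such women enter in one year than in the other, the comparison of the pregnant and non-pregnant states shifts as well. The concern is confined to the four-fold rise and makes no claim about the level of the Week 4 titre.

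**Working it through.** The protocol gives no response rate, power calculation or vaccine availability date (section 10.2 bases the sample size on feasibility), so there is no figure of its own to reproduce. The check has three parts.

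**1. Does any criterion close the gap?**

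| Provision | What it reaches | Bars a dose given more than three months earlier in the same season? |
|---|---|---|
| 5.2 item 1 | Three months back | No |
| 5.2 item 13 | 14 days back; planned vaccinations | No |
| 5.2 item 14 | 28 days back; planned vaccination | No |
| 5.2 item 19 | Investigator's opinion | Only at discretion |
| 5.1 item 3 | Gestational age | No |
| 5.1 item 4 | Medical history judged against the criteria | Adds no rule of its own |
| 7.6.3 | Five-year vaccination history | Shows the dose; attaches no rule |
| 7.6.4 | Repeats the exclusions in Year 2 | Carries the same three-month limit |

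**2. How wide is the gap in the calendar?**

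Inputs from the protocol: entry from 1 August to 31 January, which is 31 + 30 + 31 + 30 + 31 + 31 = 184 days, and a look-back of three months, taken as 92 days. Assumed input: the first day on which the season's vaccine can be had off-study.

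Count every pair of a dose day and a later entry day. A pair escapes item 1 if the interval exceeds 92 days. For availability from 1 August, the entry day *i* days after 1 August has *i* possible dose days:

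- All pairs: 1 + 2 + … + 183 = 183 × 184 / 2 = 16,836.
- Escaping pairs: *i* − 92 for each *i* from 93 to 183, so 1 + 2 + … + 91 = 91 × 92 / 2 = 4,186.
- Share: 4,186 / 16,836 = 24.9%.

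| Vaccine available from (assumed) | First entry day with a gap | Escaping pairs / all pairs | Share |
|---|---|---|---|
| 1 July | 2 October | 7,503 / 22,540 | 33.3% |
| 1 August | 2 November | 4,186 / 16,836 | 24.9% |
| 1 September | 3 December | 1,830 / 11,628 | 15.7% |
| 1 October | 2 January | 465 / 7,503 | 6.2% |

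Reading three months as 91 or 90 days changes the 1 August figure to 4,278 (25.4%) or 4,371 (26.0%). These shares count dates with equal weight, given that an earlier same-season dose occurred. They say how much of the calendar item 1 leaves open; they do not estimate a share of women.

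**3. What does one such woman do to the reported percentage?**

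Let *n* be the number analysed, *k* the number already vaccinated that season, *p* the four-fold response rate in the others and *q* the rate in those *k* women. Then:

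- Expected percentage = 100 × [(*n* − *k*)*p* + *kq*] / *n*.
- Shift from 100*p* = 100*k*(*p* − *q*) / *n*.

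The protocol gives *n* up to 50. The values *p*, *q*, *k* and *n* = 40 are assumptions. For *n* = 50, *k* = 1, *p* = 0.60 and *q* = 0.10, the shift is 100 × 0.50 / 50 = 1.0 point.

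| *n*, *k* | *p* = 60%, *q* = 10% | *p* = 40%, *q* = 30% | *p* = 80%, *q* = 0% | Ceiling (*p* = 100%, *q* = 0%) |
|---|---|---|---|---|
| 50, 1 | 1.0 | 0.2 | 1.6 | 2.0 |
| 50, 3 | 3.0 | 0.6 | 4.8 | 6.0 |
| 40, 1 | 1.25 | 0.25 | 2.0 | 2.5 |

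All entries are percentage points, downward.

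**The case against.** The strongest answer is that the case will seldom arise. The woman must have been vaccinated more than three months earlier in the same season, still be before 32 weeks of gestation, and accept a second dose that season. Section 7.6.10 lets the Year 1 dose be her routine obstetric dose, and a woman recruited that way would usually not have had it yet. At a single site with up to 50 women, the investigator will see the vaccination history and can use item 19. The planned-vaccination limb of item 13 may also catch a participant who intends an off-study dose before her Year 2 visits. Finally, a three-month window is a deliberate choice, the availability dates and response rates above are assumed, and the analysis involves no test.

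Most of this stands, and it limits the size of the point. The number affected may be zero, the date-pair shares must not be read as shares of women, and an effect on the comparison between years is conditional on unequal numbers. It does not remove the gap. Item 19 permits exclusion without requiring it. Item 13's second limb does not reach a dose already given before Year 1 entry, or an unplanned one before Year 2. The window may be deliberate, but it does not fit the protocol's own enrolment calendar. Eligibility is also fixed by the protocol: an analysis plan could describe affected women separately but could not restore their baseline.

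**Conclusion.** The concern holds and is minor. As written, the criteria can admit a woman whose Day 0 titre already reflects the current season's vaccine, in either study year. Each such woman is expected to lower that year's four-fold-rise percentage by about 1 point at *n* = 50 under the central assumption, and never by more than 2. The downward direction rests on the assumption that *q* is below *p*. The total effect depends on how many such women enter, which the protocol gives no means of estimating. The Week 4 titre level is not called into question, and no test or decision threshold is affected.

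**What to change.** Keep the three-month window in section 5.2, item 1, and add an alternative ground for exclusion: *or receipt of the current season's influenza vaccine at any time before Day 0 of that study year*. The window should stay, because replacing it would admit a woman given the previous season's vaccine shortly before an August entry.

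In section 7.6.4, state that item 1 is applied at Day 0 of both years, using the vaccination history from section 7.6.3 in Year 1 and the medical history update in Year 2. The Year 1 study dose belongs to the previous season by then, so the new clause does not exclude participants on that account.

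The cost is one clause and one clarifying sentence by amendment, and perhaps a few late-season candidates. No new data are needed.

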6 STUDY INTERVENTION/INVESTIGATIONAL PRODUCT

6.1 Study Product Description

6.1.1 Acquisition

The study product will be shipped from the manufacturer to the investigational pharmacy at the study site. IIV4 will be supplied by Glaxosmithkline Biologicals as Fluarix® Quadrivalent.

6.1.2 Formulation, Packaging, and Labeling

FDA's Vaccines and Related Biological Products Advisory Committee (VRBPAC) will make annual recommendations regarding the composition of the U.S. seasonal influenza vaccines based on global influenza virus surveillance data related to epidemiology and antigenic characteristics, serological responses to trivalent and quadrivalent seasonal vaccines, and the availability of candidate strains and reagents.

The season-specific manufacturer package inserts for each study year will be attached in the IRB protocol submissions when available.

Fluarix® Quadrivalent: Each 0.5 mL dose of Fluarix Quadrivalent (IIV4) will contain a total of 60 μg (15 μg of each strain) of influenza virus hemagglutinin of each of the 4 strains selected for the seasonal formulation. The vaccine will be supplied in a prefilled, single dose syringe, 0.5 mL (no preservative), single dose vial 0.5 mL (no preservative) or multi-dose vial, 5 mL (with preservative). Each multi-dose vial contains ten 0.5 mL doses.

6.1.3 Product Storage and Stability

Fluarix® Quadrivalent vaccine presentations should be refrigerated at 2° to 8°C (35° to 46°F). Vaccine that has been frozen will be discarded. Between uses, multi-dose vials will be returned to the recommended storage conditions at 2° to 8°C (35° to 46°F). Vaccine should not be used after the expiration date shown on the label.

6.2 Dosage, Preparation and Administration of Study Intervention/Investigational Product

IIV4 vaccine will be administered as a 0.5 mL dose, with a sterile, disposable syringe and needle by IM injection into the deltoid muscle. The participant will choose whether the injection will be administered into the right or left deltoid.

6.3 Accountability Procedures for the Study Intervention/Investigational Product(s)

The study article will be shipped by the manufacturer to the study site. Use and disposition of each unit of vaccine will be appropriately documented by the Clinical Core staff in accordance with ICH GCP. Unused products will be given to researchers.

6.4 Concomitant Medications

At entry and at each study visit, the participant will be questioned about medication use and the information will be recorded. Medication history will include vaccinations, allergy shots or PPD tests received and medications taken within 28 days prior to enrollment, as well as vaccinations, allergy shots or PPD tests received and current prescription and over-the-counter medications used throughout the study period. The investigator should be consulted regarding eligibility if the participant is taking oral steroid medications or medications for treatment of autoimmune disease (such as Plaquenil, methotrexate, prednisone, Enbrel), or any other medications which might indicate a condition that precludes participant compliance with the protocol.

7 STUDY SCHEDULE

7.1 Schedule of Events

Fuelvetion	Year 1		Year 2		Early Termination			
Evaluation	D0	D7	D28	D0	D7	D28	Visit	
Written Informed Consent	Х							
Eligibility Determination	Х							
Demographics/Medical History/Pregnancy History	Х							
Update Medical Hx/ Review Eligibility Requirements				Х				
Concomitant Medications	Х	Х	Х	Х	Х	Х	X	
Signs/Symptoms/Adverse Events	Х	Х	Х	Х	Х	Х	X	
Vital Signs/Weight	Х	If clinically	y indicated	Х	If clin indic			
Height	Х							
Hemoglobin*	Х							
Phlebotomy	Х	Х	Х	Х	Х	Х		
IIV4 Administration	Χ [†]			X				

^{*} An adequate hemoglobin level (i.e., >9.0g/dL) from within 8 weeks of entry can substitute for the research hemoglobin draw); † - IIV in Year 1 may be administered by clinic staff at Stanford Ob/Gyn Flu Clinic as part of participant's routine care (i.e., outside of research study)

7.2 Year 1, Day 0

The following will be performed at screening (see Section 7.6 for a detailed explanation of each evaluation)

- Written Informed Consent
- Eligibility Determination
- Demographics/Medical History/Pregnancy History
- Concomitant Medications
- Signs/Symptoms/Adverse Events
- Vital Signs/Weight
- Height
- Hemoglobin
- Phlebotomy
- IIV4 Administration (may be administered by clinic staff at Stanford's Ob/Gyn Clinic as part of participant's recommended obstetrical clinical care)

7.3 Year 2, Day 0 Evaluation

The following will be performed at the vaccination visit for Year 2:

- Update Medical History/Review Eligibility Requirements
- Concomitant medications
- Signs/Symptoms/Adverse Events
- Vital Signs/Weight
- Phlebotomy
- IIV4 Administration

7.4 Post-vaccination Visits

Post-vaccination visits occur following the Year 1, Day 0 Visit and the Year 2, Day 0 Visit. Week 1 visits (in both Year 1 and Year 2) occur at Day 7 (+/- 1 day) after IIV administration; Week 4 visits (in both Year 1 and Year 2) occur at Day 28 (+/- 7 days) after IIV administration.

The following will occur at each Post-vaccination Visit:

- Concomitant medications
- Signs/Symptoms/Adverse Events
- Vital Signs/Weight (only if clinically indicated)
- Phlebotomy

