7.6.7 Vital Signs and Weight

Assessment of vital signs will include measurement of resting blood pressure, pulse, respiratory rate, and temperature. Weight should be measured in kilograms.

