10 STATISTICAL CONSIDERATIONS

10.1 Study Hypotheses

We hypothesize that exposure to influenza vaccination will result in immunity to influenza in the majority of study participants and will be well-tolerated forming the basis of novel immunologic insights.

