10.3 Final Analysis Plan

We will report the percentage of participants having a 4 fold increase in HAI titers at Week 4 in Year 0 and Year 1 and the participants experiencing Grade 2 or higher AEs.

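### No capture of symptoms or temperature is specified between vaccination and Day 6-8, although the protocol expects reactions to have come and gone by then, so some Grade 2+ events risk being missed or graded too low

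*Protocol*

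**What the plan says.** **Endpoint.** Section 2 lists one secondary endpoint: "Secondary: Grade 2 or Higher Adverse Effects". Section 10.3 will report "the participants experiencing Grade 2 or higher AEs", with no test, target rate or comparison. The hypothesis in section 10.1 includes that vaccination "will be well-tolerated".

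**Expected reactions.** Section 3.1.1 (Potential Risks) states: "Vaccine recipients may develop systemic reactions such as fever, headaches, body aches, and fatigue". On timing it adds: "These reactions are usually greatest within the first 24 to 72 hours after vaccination and last 1 to 2 days".

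**When symptoms are asked about.** Section 7.1 schedules signs, symptoms and adverse events at Day 0, Day 7 and Day 28 of each year. Section 7.4 fixes the first of the post-vaccination visits: "Week 1 visits (in both Year 1 and Year 2) occur at Day 7 (+/- 1 day) after IIV administration". At that visit the list includes "Vital Signs/Weight (only if clinically indicated"). Section 7.6.7 explains what this covers: "Assessment of vital signs will include measurement of resting blood pressure, pulse, respiratory rate, and temperature".

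**Day 0.** Section 7.6.10 provides a 15-minute observation after the injection, aimed at immediate serious reactions. If the Year 1 dose is given as routine obstetric care, the same section places it after the Day 0 evaluations.

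**Scope.** Section 8.3 takes all adverse events from vaccination to four weeks afterwards. Sections 7.6.6 and 8.2 require only those of Grade 2 or higher to be recorded.

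**The concern.** The protocol says when reactions are expected and then schedules its first enquiry about them for a time when, on those figures, they are usually over. Early reactions are within the reporting window of section 8.3, so they belong to the endpoint, but they are collected in retrospect.

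Two features make this matter. First, the endpoint turns on a severity cut between Grade 1 and Grade 2. An event remembered as milder than it was need not be recorded at all, and no analysis can recover it later. Second, there is no concurrent control group, so the absolute proportion is the result. Loss by forgetting or down-grading lowers that proportion, which is the direction that favours the tolerability hypothesis.

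Fever is the weakest case. It is the first systemic reaction that section 3.1.1 names, and the protocol arranges no temperature measurement on the days when it would be expected.

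**Working it through.** The protocol states no power, error rate or expected event rate (section 10.2 rests the sample size on feasibility), so there is no figure of its own to reproduce. The check is on days.

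**Inputs from the protocol**
- Peak of systemic reactions: 24-72 hours, that is Day 1 to Day 3 (section 3.1.1).
- Duration: 1 to 2 days (section 3.1.1).
- First scheduled enquiry after the vaccination visit: Day 7 +/- 1, that is Day 6 to Day 8 (sections 7.1 and 7.4).

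**Gap from peak to enquiry**
- Shortest: 6 - 3 = 3 days.
- Longest: 8 - 1 = 7 days.

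**Gap from resolution to enquiry**, counting the duration from the peak
- Resolution: from 1 + 1 = Day 2 to 3 + 2 = Day 5.
- Shortest gap: 6 - 5 = 1 day.
- Longest gap: 8 - 2 = 6 days.

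A usual reaction is over before the enquiry under every combination. Counting the duration from onset instead of from the peak could only move resolution earlier.

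**Does anything fill the gap?** The schedule (7.1), the visit list (7.4) and the adverse-event procedure (7.6.6) name no diary, telephone call or home temperature. In the Day 0 lists (7.2 and 7.3) symptoms stand before vaccine administration. The 15-minute observation ends long before 24 hours. A temperature taken at Day 7 would in any case usually come after the fever.

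**Illustration of size.** The true rate and the share captured are assumptions; only n = 50 comes from the protocol, as the maximum enrolment.

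Expected count = 50 x true rate x share captured. Chance of seeing no event = (1 - true rate x share captured)^50.

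| True rate | Share captured | Expected count | Chance of no event |
|---|---|---|---|
| 5% | 100% | 2.5 | 7.7% |
| 5% | 90% | 2.25 | 10.0% |
| 5% | 70% | 1.75 | 16.8% |
| 5% | 50% | 1.25 | 28.2% |
| 10% | 100% | 5.0 | 0.5% |
| 10% | 90% | 4.5 | 0.9% |
| 10% | 75% | 3.75 | 2.0% |
| 10% | 50% | 2.5 | 7.7% |
| 20% | 100% | 10.0 | <0.1% |
| 20% | 50% | 5.0 | 0.5% |

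At a true rate of 10% and 70 to 90% capture, the loss is 5 x (1 - 0.9) = 0.5 to 5 x (1 - 0.7) = 1.5 events, and the reported rate is 7 to 9%. The table treats the endpoint as if it consisted of early reactions only. Section 8.3 counts all events for four weeks, so the proportional loss in the whole endpoint would be smaller.

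**The case against.** The strongest case against runs as follows.

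- **The protocol is silent on the tool.** Source forms or site procedures may provide one. This stands as a limit on wording: a reader might infer that symptoms are collected from unaided memory, but the protocol neither provides an aid nor rules one out. What can be said is that none is specified.
- **Recall may be adequate.** It covers about a week, and Grade 2 or higher events are easier to remember than mild ones. Section 7.6.5 has staff record medication changes at Day 7, and section 3.1.1 mentions analgesics for these reactions, so that question is a partial prompt. This stands too, although a medication entry gives neither severity nor temperature. It is why an under-count is a risk and not an established fact.
- **Fever can still be graded** if a woman took her temperature at home and reports it. A reader might conclude that grading is impossible. The protocol does not support that, and it does not reproduce the fever thresholds of the grading scale it cites.
- **The illustrated loss is small against sampling error.** The exact 95% interval for 5 of 50 is about 3% to 22%, and no decision threshold exists. This is correct, but a wide interval does not reflect a systematic shift.
- **Bias between pregnant and non-pregnant years is speculative.** A reader might suppose that women attend to symptoms differently in the two states. Nothing in the protocol shows it: both years use the same schedule, and no comparison of adverse events between years is planned.
- **Proportion.** This is a small single-site study of a licensed vaccine with a serological primary endpoint, which is untouched. Visit-based collection is a defensible choice. That limits the weight of the point but does not remove it.

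**Conclusion.** The point holds as a risk to the secondary endpoint. On the protocol's own figures the first scheduled symptom enquiry after the vaccination visit comes 3 to 7 days after the peak and about 1 to 6 days after a usual reaction has ended, with nothing specified in between. Some Grade 2+ reactions may be missed or graded too low, and the grading of fever rests on unsolicited home readings. The expected direction is downward. The size depends on a true rate and a recall share that the protocol does not give; over the assumed ranges above it runs from a fraction of one event to 5 of 10. The timing result assumes that the duration in section 3.1.1 describes the usual reaction, as that section says. The primary endpoint is not affected and the study is not invalidated: this is a cheap improvement to data collection.

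**What to change.** At Day 0 in both years, including when the Year 1 dose is given in the obstetric clinic, hand each participant a one-page symptom memory aid for Days 0 to 7. It should ask for the date, the symptom, its worst severity, and a temperature if she feels feverish. Review it and assign the grade at the existing Day 7 visit. Add a row to the schedule in section 7.1 and a line to section 7.6.6.

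**Cost.** One form, a small IRB amendment, a few minutes at a visit that already takes place, and slight participant burden. No new visit, staff or blood is needed. The reported Grade 2+ percentage may rise.

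**Condition.** The aid should be used alike in both years. If it is introduced after some women have completed Year 1, report the adverse-event percentage by collection method and do not compare the years in those women, because the change of method would itself create a difference.
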